3.3 Secondary Objective: Mortality

The secondary objective is to compare the mortality rates for patients meeting 1.5 prevention criteria between those implanted with a device (ICD/CRT-D) and those not implanted.

Hypothesis

Although this is an exploratory objective and is not powered, a hypothesis test will be done and compared to an alpha level of 0.05.

H_0 : Hazard ratio of non-implanted to implanted 1.5 patients = 1

H_a : Hazard ratio of non-implanted to implanted 1.5 patients $\neq 1$

Analysis Methods

A Cox proportional hazards model will be used to compare the mortality rates between subjects with device implant and without, in subjects who meet the 1.5 prevention criteria. In addition to the implant/no implant variable, the Cox proportional hazards model will include baseline covariates that are known to be associated with mortality and that might be unbalanced between the groups due to the non-randomized study design. These covariates are:

- age at consent
- sex
- QRS duration
- ischemic cardiomyopathy (yes/no)
- left bundle branch block (LBBB) (yes/no)
- NYHA Classification (treated as an ordinal variable, including 0 for those without HF)
- diabetes (Type 1 or 2 only, gestational not counted) (yes/no)
- LVEF (taken from the 1.5 Visit CRF, if it exists, or from the Baseline CRF)
- syncope qualifying as 1.5 (yes/no)
- NSVT qualifying as 1.5 (yes/no)
- PVCs qualifying as 1.5 (yes/no)

Note that all 3 categorical 1.5 covariates can be found at the end of the 1.5 Criteria CRF. The NSVT and PVC variables on the Baseline CRF do not include the minimum thresholds of 3 consecutive >100 bpm beats for NSVT and 10 or more PVCs per hour.

Country of enrollment was to be included as a covariate according to the CIP, but it will not be included as subjects in the study (who all have medical care) may not have significantly different mortality rates between countries. Also, some countries may have a small number of enrollments. The idea was to have covariates with known mortality risks.

LBBB and diabetes are added covariates from the CIP based on steering committee input. LBBB was added because it is a well-known mortality risk factor. Diabetes was not originally collected in the study, but was added later and is being collected for all subjects, including those enrolled prior to it being added to the Medical History CRF.

Due to the large sample size, it is likely that some subjects will have covariates missing. To circumvent this problem, multiple imputation methods will be used. More specifically:

- The number of imputed datasets to be created will be 20.
- The imputation of missing values will be done using the fully conditional specification (FCS) method, where the covariates in the imputation model are the same covariates in the Cox proportional model (except the covariate being imputed) plus implant/no implant, the event indicator and the Nelson-Aalen estimator of the cumulative hazard function as suggested by White and Royston (2009).
- The imputation for missing binary variables (e.g., gender) will be done via the FCS logistic regression method, and for missing continuous variables (e.g., QRS) it will be done via the FCS linear regression method.
- Missing NYHA will be imputed via FCS ordinal logistic regression.
- All continuous variables will be standardized before the imputation phase, in order to avoid the FCS linear regression imputing values that are not realistic (e.g., negative LVEF).
- The null hypothesis will be rejected if the pooled p-value for the implant/no-implant covariate is less than 0.05.

The analysis will be performed using SAS code similar to:

```
/*Nelson-Aalen Estimates for Cumulative Hazard Function*/  
  
proc phreg data=alldataneeded1p5 noprint;  
  model SURVTIME*EVENT(0) =;  
  output out=alldataneeded1p5_2 logsurv=logs / method=emp;  
run;  
  
data Alldataneeded1p5_2;  
  set Alldataneeded1p5_2;  
  cumhaz = -logs;  
run;  
  
proc standard data = Alldataneeded1p5_2 mean = 0 std=1 out=  
Alldataneeded1p5_3;  
  var AGE LVEF0 QRS;  
run;  
  
/*Imputation Phase*/  
proc mi data= Alldataneeded1p5_3 n impute = 5 out = mi_alldata_1p5 ;  
class SEXCHAR CMYISCH LBBB NYHA0 DIABETES CRIT15SYNC CRIT15NSVT CRIT15PVC  
GROUP EVENT;  
var AGE SEXCHAR QRS CMYISCH LBBB NYHA0 DIABETES LVEF0 CRIT15SYNC CRIT15NSVT  
CRIT15PVC GROUP CUMHAZ EVENT;  
fcs logistic(SEXCHAR CMYISCH LBBB NYHA0 DIABETES CRIT15SYNC CRIT15NSVT  
CRIT15PVC GROUP EVENT);  
run;  
  
/*Analysis Phase*/  
proc phreg data = mi_alldata_1p5;  
class SEXCHAR CMYISCH LBBB NYHA0 DIABETES CRIT15SYNC CRIT15NSVT CRIT15PVC  
GROUP EVENT;
```

```

model SURVTIME*EVENT(0) = AGE SEXCHAR QRS CMYISCH LBBB NYHA0 DIABETES LVEF0
CRIT15SYNC CRIT15NSVT CRIT15PVC GROUP ;
by _Imputation_;
ods output ParameterEstimates=coxReg_fcs;
ods output Type3=type3table;
run;

/*Pooling Phase*/
proc mianalyze parms(classvar=ClassVal) = coxReg_fcs;
class SEXCHAR CMYISCH LBBB NYHA0 DIABETES CRIT15SYNC CRIT15NSVT CRIT15PVC
GROUP;
modeleffects AGE SEXCHAR QRS CMYISCH LBBB NYHA0 DIABETES LVEF0 CRIT15SYNC
CRIT15NSVT CRIT15PVC GROUP ;
run;

```

Kaplan-Meier estimates of the survival curves will be displayed for each group.

The same analysis will be performed comparing implanted and not implanted 1.0 subjects.

Time to Event Considerations

- Time 0 is the enrollment date and subjects will be censored on the last date they were confirmed to be alive.
- Non-implanted patients that later decided to implant the ICD/CRT-D, will have their time to event censored at the day of the implant procedure.
- Implanted patients that explanted the device (without replacement) will continue to be followed as part of the implanted group. These cases will be rare, and unless the explant is completely voluntary (i.e., not due to infection, or imminent subject end-of-life), censoring subjects at explant would bias the results in favor of implant. This is an intention-to-treat approach.
- Patients that had heart transplant will have their time to event censored at the day of the transplant.

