2.3 Non-sustained ventricular tachycardia (NSVT)

Ventricular tachycardia (VT) is a rapid heartbeat originating in the ventricles. VT is potentially life-threatening because it may lead to ischemia, ventricular fibrillation (VF), asystole, and sudden cardiac death. In this study, VT is defined as three or more consecutive ventricular beats at a rate of more than 100 beats per minute. Non-sustained ventricular tachycardia (NSVT) is VT which spontaneously terminates within 30 seconds. Otherwise the VT is defined as sustained VT.

A meta-analysis of 11 studies (published from 1989 - 2007; N=4387) found NSVT to be a statistically significant predictor for arrhythmic events in patients with LV dysfunction.¹¹

An analysis by Moore et al. of the SCD-HeFT trial looked at overall mortality by NSVT episode frequency. They found that in 673 patients who had NSVT, 271 had 1 NSVT and 402 had ≥1 NSVT episodes on baseline Holter Monitor. The authors concluded that the presence of ≥2 NSVT episodes conferred an increased overall mortality when compared to less frequent NSVT episodes.¹²

A Canadian trial that looked at predictors of appropriate ICD therapy in patients receiving primary prevention ICDs showed that ICD therapy occurred in 19% of 421 primary prevention patients with both ischemic and non-ischemic cardiomyopathy and was predicted most strongly by NSVT and a lack of beta blocker use.¹³

Results from 1135 primary prevention patients from the OMNI study showed a significant correlation between presence of device-detected NSVT and true VT/VF episodes.¹⁴ The vast majority of (91.3%) patients with true VT/VF episodes also

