6.14 Medications

Cardiovascular medication categories specific for systolic heart failure will be collected at the baseline visit for characterization of the population, including:

- Anti-arrhythmics
- Anticoagulants
- ACE Inhibitors
- Angiotensin II Receptor Blockers/Inhibitors
- Diuretics
- Vasodilators

It is expected that patients will be on chronic, guideline-directed medical therapy at baseline (e.g., Beta Blockers, ACE inhibitors minimally); this is consistent with both the ACC/AHA/HRS and ESC Guidelines. Following device implant, Amiodarone should be discontinued for subjects taking it prophylactically (e.g., for preventative reasons). Amiodarone use for symptom control is permitted. Subjects will be asked at follow-up visits if they are taking Amiodarone. No other medication changes will be tracked throughout the study.

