3.1.1 Description of Baseline Variables

A number of characteristics will be reported for each enrolled subject at time of enrollment. The variables collected will include demographics, medical history, NYHA classification, and cardiovascular medications. Tables and descriptive statistics will be used to summarize subject data with respect to these variables.

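### The non-randomized mortality model adjusts for no baseline heart-failure medication, although these drugs are collected and meet the SAP's own rule for choosing covariates

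*SAP*

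**What the plan says.** SAP 3.3 tests the null "Hazard ratio of non-implanted to implanted 1.5 patients = 1" in a Cox model against a two-sided alternative; "a hypothesis test will be done and compared to an alpha level of 0.05". Because subjects choose whether to be implanted, the model is to include "baseline covariates that are known to be associated with mortality and that might be unbalanced between the groups due to the non-randomized study design". The list is age, sex, QRS duration, ischemic cardiomyopathy, LBBB, NYHA class, diabetes, LVEF, and qualifying syncope, NSVT and PVCs. The SAS code for imputation, analysis and pooling uses the same set. SAP 3.3 also says the analysis will be run again for implanted and non-implanted 1.0 subjects.

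Medication is collected at baseline (Protocol 6.4 Table 7, 6.6 and 6.14). SAP 3.1.1 puts it among the descriptive baseline variables: "The variables collected will include demographics, medical history, NYHA classification, and cardiovascular medications". Protocol 6.14 names six categories: anti-arrhythmics, anticoagulants, ACE inhibitors, angiotensin receptor blockers, diuretics and vasodilators. Beta blockers are not among them, although the same section says: "It is expected that patients will be on chronic, guideline-directed medical therapy at baseline (e.g., Beta Blockers, ACE inhibitors minimally".

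Protocol 12.3.2 has no drug in its covariate list either, but lets the SAP add baseline covariates before any analysis. The SAP used that freedom to add LBBB and diabetes and to drop country.

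**The concern.** Background drug therapy is the kind of factor the SAP's rule describes: a baseline characteristic plausibly related to death that may differ between people who accept and people who decline a device. Guideline therapy is expected but is not an inclusion criterion (Protocol 5.2.1), so it can vary.

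The plan's own figures also suggest that implant status follows care setting. The comments in the SAP appendix program assume that 30% of 1.5 subjects are implanted in China, 40% in India and 65% elsewhere. Country, the one term that could have stood in for setting, was removed. NYHA class and LVEF describe disease status, not treatment.

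If drug use differs by arm after the listed covariates, the model has nowhere to put the difference except the implant term. A nominally significant mortality result could then partly reflect medical therapy, or a real device effect could be understated.

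**Working it through.** **1. The plan's own figure.** Protocol Table 10 and SAP 3.3.1 give 88% log-rank power for 450 implanted and 550 non-implanted subjects with 3-year mortality of 18% and 26%. I took exponential survival, 2 years of uniform accrual, 2 further years of follow-up and no attrition.

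- HR = ln(1 − 0.18)/ln(1 − 0.26) = 0.659.
- Deaths per group = n × {1 − [exp(−2λ) − exp(−4λ)]/(2λ)}, with λ = −ln(1 − 3-year mortality)/3. This gives about 81 + 142 = 223.
- Power = Φ(|ln 0.659| × √(223 × 0.45 × 0.55) − 1.96) = Φ(1.14) = 87.2%.

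The figure reproduces. It is for an unadjusted test, and the plan says the effect of covariates on power is not known, so nothing below changes it.

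**2. Precision at the expected group sizes.** SAP 3.3.1 expects 430 implanted and 540 non-implanted 1.5 subjects. With a common 3-year mortality of 22% (rounded from the 18.5% and 25.7% quoted there), λ = 0.0828 and deaths = 970 × 0.219, about 213. The implanted fraction is 430/970 = 0.443. SE(log HR) = √(1/(213 × 0.443 × 0.557)) = 0.138.

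**3. Effect of one omitted drug class.** The documents give neither drug use by arm nor a drug effect on mortality, so these inputs are assumptions. Let g be the mortality hazard ratio on versus off the drug, and let use be p₁ in implanted and p₀ in non-implanted subjects. Take the drug as independent of the listed covariates and the true device effect as nil. Then

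spurious HR (non-implanted to implanted), b = (1 − p₀ + p₀g)/(1 − p₁ + p₁g)

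two-sided error = Φ(−1.96 + |ln b|/SE) + Φ(−1.96 − |ln b|/SE)

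| g | p₁ | p₀ | b | Two-sided error |
|---|---|---|---|---|
| any | 85% | 85% | 1.00 | 5.0% |
| 0.85 | 85% | 75% | 0.8875/0.8725 = 1.017 | 5.2% |
| 0.75 | 85% | 65% | 0.8375/0.7875 = 1.063 | 7.3% |
| 0.65 | 85% | 55% | 0.8075/0.7025 = 1.149 | 17.2% |
| 0.85 | 75% | 85% | 0.8725/0.8875 = 0.983 | 5.2% |
| 0.65 | 75% | 85% | 0.7025/0.7375 = 0.953 | 6.4% |

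Other assumed inputs fall inside this range. With use of 90% versus 80% and a hazard of 1.3 off the drug, b = 1.06/1.03 = 1.029. With 90% versus 70% and 1.5, b = 1.15/1.05 = 1.095.

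**4. Yardstick.** The retrospective figures in SAP 3.3.1 imply HR = ln(1 − 0.257)/ln(1 − 0.185) = 1.45. On the log scale the largest value in the table is ln 1.149/ln 1.452 = 0.139/0.373, about 37% of that.

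**5. Confounder or mediator?** Time 0 is enrollment, medications are baseline data, and SAP 3.1.2 excludes subjects whose Baseline or Medical History CRF is dated after implant. Baseline drug use therefore precedes the device, and adjusting for it does not remove part of the device's effect.

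**The case against.** The strongest reply is that nothing shows an imbalance. Protocol 6.14 expects guideline therapy in everyone, entry requires a Class I indication, SAP 3.3 remarks that all subjects have medical care, and non-implantation is described as the patient's choice. NYHA class, LVEF, diabetes, ischemia and age may absorb some of any difference. This stands as far as direction and size go. A reader might infer that non-implanted subjects are worse treated and that the device gets the credit. No section says so, and the reverse imbalance would count against the device.

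A reader might also infer that beta blockers are not collected. Protocol 6.14 introduces its categories with the word including, so the list may not be complete, and the CRFs are under separate cover (Protocol Appendix D). Beta blockers could have their own field or be recorded under another category. Nor does Protocol 2.3 show that they confound mortality. The finding cited there, that appropriate ICD therapy "was predicted most strongly by NSVT and a lack of beta blocker use", concerns device therapy in ICD recipients, not death and not implanted versus non-implanted patients.

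The SAP also says of the test: "Although this is an exploratory objective and is not powered". Protocol 12.3.1 makes it valid only if the primary endpoint succeeds, and the SAP allows analyses beyond the plan. This lowers the stakes. It does not explain why a recorded variable that fits the stated rule is left out of a model tested at 0.05.

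**Conclusion.** The omission is real: no baseline drug enters the Cox or imputation model, for 1.5 or for 1.0 subjects, although drug classes are collected and fit the SAP's rule. The consequence is conditional. If use differs by implant status given the listed covariates, the implant hazard ratio absorbs the difference, in a direction the documents do not show.

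For one drug class in the 1.5 comparison the assumed inputs give 1.02 to 1.15 when non-implanted subjects use less, with error of about 5% to 17%; nothing when use is equal; and 0.95 to 0.98 when the imbalance is reversed. The low end is negligible. The high end could tip a borderline p-value but would not by itself produce the 1.45 implied by the planning data. The range rests on assumed use and drug effects, on independence from the other covariates and on about 213 deaths. The documents give no mortality figure for 1.0 subjects, so that comparison is not sized.

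This should be changed because the correction is cheap and the comparison is not randomized. It is not evidence that the planned result will be biased toward the device.

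**What to change.** - Add the baseline drug classes already collected to the SAP 3.3 covariate list, the Cox model and the FCS imputation model, for both the 1.5 and 1.0 comparisons. At a minimum add ACE inhibitor or ARB (yes/no).
- Add anti-arrhythmic and diuretic use either as further baseline terms or in a stated sensitivity analysis. They may mark severity or indication as much as quality of treatment, so the choice should be made before analysis.
- Tabulate baseline drug use by implant status, so that readers can see whether an imbalance exists and which way it runs.
- Confirm whether the CRF records beta blockers. If it does, add them as a covariate. If not, collect baseline use from records for all subjects. The SAP gives the precedent: "Diabetes was not originally collected in the study, but was added later and is being collected for all subjects".

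Protocol 12.3.2 already permits added baseline covariates before any analysis. The cost is a few model terms: the present 11 covariates plus implant status make 12, and four more would make 16, against about 213 expected deaths in the 1.5 comparison (213/16, about 13 per term, counting each covariate once). Retrospective beta-blocker collection is needed only if the CRF lacks it. The estimated device effect may become slightly smaller.

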12.3.1 Hypothesis

Although this is an exploratory objective and is not powered, a hypothesis test will be done and compared to an alpha level of 0.05. To preserve overall type I error, this test is only valid if the primary endpoint is statistically significant.

Compare the mortality rates for patients meeting 1.5 prevention criteria between those implanted with a device (ICD/CRT-D) and those not implanted.

H_0 : Hazard ratio of non-implanted to implanted 1.5 patients = 1

H_A : Hazard ratio of non-implanted to implanted 1.5 patients $\neq 1$

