1 PURPOSE

This Statistical Analysis Plan has been designed to document, before data is analyzed, the rationale for the study design, and the planned analyses that will be included in study reports. This plan does not limit the analysis provided in reports, and additional analysis of the study data beyond this plan is expected.

The Statistical Analysis Plan was developed based on version 1.0 of the Improve SCA Study Clinical Investigation Plan dated December 23, 2013.

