3.1.3 Reports for which this Statistical Analysis Plan applies

This analysis plan shall apply to the final report. Statistical analysis for study related publications will not be limited to this plan. However, it is the intent that the main study publication will follow the methods detailed in this plan, which in some cases supersede the investigational plan.

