3.3.2 Determination of Patients/Data for Analysis

All subjects in the 1.5 prevention cohort at the time of enrollment who do not meet the criteria in section 3.1.2 of this document will be included. The same criteria apply for the 1.0 subjects in their mortality analysis.

Hypothesis

Although this is an exploratory objective and is not powered, a hypothesis test will be done and compared to an alpha level of 0.05.

H_0 : Hazard ratio of patients with Chagas disease to patients without Chagas disease = 1
 H_a : Hazard ratio of patients with Chagas disease to patients without Chagas disease \neq 1

Only subjects with implant (regardless the prevention criteria group) will be included in the analysis. Subjects with missing information regarding Chagas disease will not be included.

The hypothesis will be tested separately for 1.0, 1.5, and secondary groups.

Analysis Methods

A Cox proportional hazard model will be used to compare the hazard rates of first appropriate VT/VF therapy between subjects with Chagas disease and subjects without Chagas disease within each group (1.0, 1.5, and secondary). The Cox proportional hazards model will only include the Chagas disease indicator. The null hypothesis will be rejected if the p-value for the Chagas disease indicator covariate is less than 0.05.

The analysis will be performed using SAS code similar to:

```
proc phreg data=alldataneeded ;
  class chagas;
  model firstVTVFappropTreat*event(0) = chagas;
run;
```

Time to Event Considerations

- Time 0 is the implant date and, if no events occur, subjects will be censored on the date of their latest device interrogation. Only spontaneous, appropriately treated VT/VF episodes as adjudicated by the episode review committee will count toward the endpoint.
- VT/VF episodes that cannot be adjudicated (due to not saving full episode data or any other reason) will be ignored. Often, these episodes are followed by episodes that can be adjudicated, and since the endpoint is time to first episode, effects on the results from these events will be minimal. In addition, these should be balanced between the comparison groups.

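### SAP 3.3 repeats the mortality test in 1.0 subjects with a 0.05 rejection rule but gives it no place in the protocol's testing order

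*SAP*

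**What the plan says.** Protocol 12.3 contains one mortality comparison, implanted against non-implanted 1.5 subjects, tested two-sided at 0.05. Protocol 12.3.1 calls it exploratory and unpowered, and still controls it: "To preserve overall type I error, this test is only valid if the primary endpoint is statistically significant".

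SAP 3.3 keeps the label and the alpha: "Although this is an exploratory objective and is not powered, a hypothesis test will be done and compared to an alpha level of 0.05". Its null names 1.5 patients only: "Hazard ratio of non-implanted to implanted 1.5 patients = 1". It does not repeat the protocol's condition on the primary. The decision rule is: "The null hypothesis will be rejected if the pooled p-value for the implant/no-implant covariate is less than 0.05". After the SAS code comes one further sentence: "The same analysis will be performed comparing implanted and not implanted 1.0 subjects". SAP 3.3.2 confirms that this is a separate analysis with its own population: "The same criteria apply for the 1.0 subjects in their mortality analysis".

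No visible passage writes a null hypothesis for the 1.0 comparison, gives it an alpha or a place in the order, or calls it descriptive. SAP 3.1.3 intends the main publication to follow the SAP's methods, "which in some cases supersede the investigational plan".

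**The concern.** Repeating an analysis whose last step is a rejection rule repeats the rejection rule. The protocol's chain has two links, the primary and then 1.5 mortality, and the 1.0 comparison belongs to neither. Someone following the SAP literally could therefore report a significant device association with mortality in 1.0 subjects when the primary has failed and the 1.5 mortality test is, by the protocol, not valid. That defeats the purpose the protocol gives for its condition. Restoring the condition for the 1.5 test alone would leave this route open.

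The sentence also needs rewriting for another reason. By definition 1.0 subjects meet no 1.5 criterion, so the three covariates for qualifying syncope, NSVT and PVCs take the value no for all of them. Those terms cannot be estimated, and the model cannot be the same one.

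**Working it through.** **Inputs**
- Primary: one-sided 5% test (SAP 3.2), 80% power at 4,800 subjects (Protocol 12.2.6; 80.4% in the SAP appendix).
- 1.5 mortality: two-sided 0.05, valid only after a significant primary (Protocol 12.3.1).
- 1.0 mortality: the same 0.05 rule, carried over by the added sentence, with no condition.
- Group sizes: 4,800 × 0.40 × 0.50 = 960 in each primary prevention group. Implant shares of 45% and 22% give 432/528 (1.5; the documents say about 430 and 540) and 211/749 (1.0).

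**Reproducing the plan's figures.** Log-rank power = Φ(|ln HR| × √(D·p·(1 − p)) − 1.96), where D is deaths and p the implanted share. For 450 against 550 with 3-year mortality of 18% and 26%: D = 450 × 0.18 + 550 × 0.26 = 224, HR = ln 0.82 / ln 0.74 = 0.659, p = 0.45, power 87.4%. Protocol Table 10 states 88%. Of its 20 cells, 18 agree within 2 points and the others miss by 2.2 and 3.0. Rebuilding the appendix simulation at 4,800 subjects (4,000 runs) gave primary power of 81.8%. The design inputs are therefore understood.

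**Any false rejection over the three tests, all nulls true.** In the protocol's chain nothing can be rejected unless the primary is, so the error is 5% whatever the correlation between the primary and 1.5 mortality. The 1.5 and 1.0 cohorts share no subjects, and 1.0 subjects are outside the primary comparison. A few enrolled as 1.0 may be implanted later as 1.5 and enter the primary, but their mortality time is censored at that implant, where their primary time starts. The 1.0 test is therefore treated as independent of the chain:

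1 − (1 − 0.05)(1 − 0.05) = 9.75%.

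**False mortality rejections only, both mortality nulls true, condition kept on 1.5.** Let g be the chance that the primary rejects, taken as independent of the 1.5 mortality test. The error is 1 − (1 − 0.05g)(1 − 0.05).
- g = 0.80 (design power): 1 − 0.96 × 0.95 = 8.8%.
- g = 0.05 (primary null true): 1 − 0.9975 × 0.95 = 5.2%.
- g = 1: 9.75%. In 20,000 simulated pairs of null log-rank tests, at least one rejected in 9.9% and the 1.5 test alone in 5.0%.

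**Remedies compared**
- 1.0 reported without a test: at most 5% overall.
- Fixed sequence primary, 1.5, 1.0: at most 5% overall. With g = 0.80 and both mortality nulls true, 0.80 × 0.05 = 4.0%.
- Both mortality tests conditional on the primary but unordered: 0.80 × 0.0975 = 7.8% false mortality rejections, so a condition alone is not enough.
- Bonferroni, 0.025 each: 1 − 0.975² = 4.94% for the two mortality tests. At 432/528 with 26% against 18%, 1.5 power falls from 86.0% to 78.8%.

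**Illustration for the conditional part of the fix.** Suppose the true hazard ratio is 0.659 in both cohorts. Power is 86% in 1.5. In 1.0 it is 75% down to 37% if 3-year mortality without a device is 26% down to 10%; this range is assumed, because the documents give no 1.0 mortality. Significance in 1.5 but not in 1.0 then occurs in 0.86 × (1 − 0.75) ≈ 22% to 0.86 × (1 − 0.37) ≈ 54% of trials with no true difference.

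**The case against.** The strongest reply is that no second confirmatory test exists. The only mortality null in the SAP names 1.5 patients, and the rejection sentence refers to that null. Where the SAP wants group-by-group tests it says so, as in the Chagas analysis. If the added sentence carries over the p-value rule, it should also carry over the exploratory label and, arguably, the protocol's condition. SAP 1 announces further analyses in any case: "This plan does not limit the analysis provided in reports, and additional analysis of the study data beyond this plan is expected". Part of this stands: the 1.0 test is implied and not written out, and the surrounding objective is exploratory. It does not settle the matter, because the protocol gave the same exploratory objective a type I error condition, and the SAP neither repeats the condition nor says whether it reaches the 1.0 comparison.

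Three stronger readings are tempting, and the documents do not support them.
- A reader might infer that a mortality family runs at about twice its stated alpha. No family-wise alpha is set for mortality. The 0.05 belongs to the single 1.5 test, whose own error stays at 5%.
- A reader might infer that the SAP has abolished the condition altogether, which would give 1 − 0.95³ = 14.3% over three independent tests. SAP 3.3 explains its covariate changes from the protocol and announces no such change, so its silence is an omission to correct.
- A reader might infer that the plan will contrast 1.5 and 1.0 device effects by comparing two p-values. No visible sentence plans that contrast; it is a foreseeable misreading of results placed side by side.

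Some objectives are redacted in both documents, so a status given to the 1.0 analysis there cannot be excluded.

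**Conclusion.** The point holds as a minor to moderate one. As the visible text stands, the 1.0 mortality comparison inherits a 0.05 rejection rule and lies outside the protocol's testing order, so it could be declared significant after a failed primary. The error over the primary, the conditional 1.5 test and the unconditional 1.0 test is 9.75% against the 5% the chain would otherwise hold. That figure assumes that all three nulls are true and that the 1.0 test is independent of the others. The 8.8% and 5.2% for false mortality rejections further assume that the primary result and the 1.5 mortality test are independent. The 22% to 54% illustration is not an error rate of any planned test; it shows only why two p-values would be a poor basis for a contrast.

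**What to change.** In SAP 3.3, restate the protocol's condition that the 1.5 mortality test is valid only if the primary is significant. Then replace the sentence on 1.0 subjects with one of two options.
1. Report the adjusted hazard ratio and 95% CI in 1.0 subjects descriptively, with no hypothesis test and no claim.
2. Test 1.0 mortality third in a fixed sequence (primary, 1.5 mortality, 1.0 mortality), each step only if the one before is significant.

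Under either option, list the covariates for the 1.0 model without the three qualifying-criterion indicators.

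If, and only if, a difference in device association between 1.5 and 1.0 subjects will be claimed, prespecify a pooled Cox model with an implant-by-group interaction and rest the claim on that estimate and its CI.

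The cost is a few sentences and at most one extra model on data already collected, with no more subjects and no loss of 1.5 power. The sponsor gives up a stand-alone significance claim for 1.0 mortality, and the interaction estimate would be imprecise.
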